## 6.3 Participant numbering, treatment assignment, randomization

### 6.3.1 Participant numbering

All participants derived from the EHR database will receive an invitation from their treating physician to be involved in a clinical trial and to have an in-person screening visit at the investigator site. Each potential participant who agrees to participation will be identified in the study by a Participant Number (Participant No.), that is assigned when the participant is enrolled for screening and is retained for the participant throughout his/her participation in the trial. A new Participant No. will be assigned at every subsequent enrollment if the participant is re-screened. The Participant No. consists of the Center Number (Center No.) (as assigned by Novartis to the investigative site) with a sequential participant number suffixed to it, so that each participant’s participation is numbered uniquely across the entire database. Upon signing

the informed consent form, the participant is assigned to the next sequential Participant No. available.

A new ICF will need to be signed if the investigator chooses to re-screen the participant after a participant has screen failed, and the participant will be assigned a new Participant No.

### **6.3.2 Treatment assignment, randomization**

At visit 2, all eligible participants will be randomized via Interactive Response Technology (IRT) to one of the two treatment groups in 1:1 ratio ("inclisiran first" implementation strategy or usual care). The investigator or his/her delegate will contact the IRT after confirming that the participant fulfills all the inclusion/exclusion criteria. The IRT will assign a randomization number to the participant, which will be used to link the participant to a treatment group and will specify a unique medication number for the first package of study treatment to be dispensed to the participant.

The randomization numbers will be generated using the following procedure to ensure that treatment assignment is unbiased. A participant randomization list will be produced by the IRT system provider using a validated system that automates the random assignment of participant numbers to randomization numbers. These randomization numbers are linked to the different treatment groups, which in turn are linked to medication numbers. A separate medication list will be produced by or under the responsibility of Novartis Drug Supply Management using a validated system that automates the random assignment of medication numbers to the package containing the investigational drug(s).

Randomization will be stratified by [REDACTED]. The stratification ensures balanced allocation of participants to treatment groups within the [REDACTED] strata.

The randomization scheme for participants will be reviewed and approved by a member of the Novartis Biometrics group.

### **6.4 Treatment blinding**

Not applicable.

### **6.5 Dose escalation and dose modification**

Dose interruptions for the investigational study medication (inclisiran) are not permitted.

If a planned dose is missed by less than 3 months, administer inclisiran and maintain dosing according to the participant's original schedule. If a planned dose is missed by more than 3 months, start a new dosing schedule - administer inclisiran initially, again at 3 months, and followed by every 6 months.

Dose interruptions must be recorded on the inclisiran Dose Administration case report form for the investigational study drug.

#### **6.5.1 Dose modifications**

Study drug administration of inclisiran [inclisiran (KJX839), 284 mg liquid in PFS, 1.5 ml] should be temporarily interrupted or permanently discontinued in participants with:

1. Intolerable AEs, or if the investigator believes that continuing dosing will be detrimental to the participant's mental or physical health. This includes severe or serious reactions at the injection site and any anaphylactic type reactions.
2. Liver laboratory values meeting the study drug interruption criteria listed in Table 16-4 and Table 16-5.
3. Unexplained creatine phosphokinase (CPK) values  $>5 \times$  ULN confirmed by repeat test when the CPK elevation is associated with muscle pain, muscle tenderness and/or muscle weakness, or new onset renal dysfunction.

Study treatment may be restarted at the discretion of the investigator, if the reason for discontinuation has resolved.

The dose interruptions must be recorded on an appropriate eCRF.

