Following appropriate causality assessments, as outlined above, the causality of the treatment is estimated as “probable” i.e. >50% likely, if it appears greater than all other possible causes of liver injury combined. The term “treatment-induced” indicates *probably caused* by the treatment, not by something else, and only such a case can be considered a DILI case and should be reported as an SAE.

All cases confirmed on repeat testing meeting the laboratory criteria defined above, with no other alternative cause for LFT abnormalities identified, should be considered as “medically significant,” and thus, meet the definition of SAE and should be reported as SAE using the term “potential treatment-induced liver injury.” All events should be followed up with the outcome clearly documented.

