**Table 16-4 Follow up requirements for liver laboratory triggers with liver symptoms**

ALT or AST	TBL	Liver Symptoms	Action
ALT or AST increase without bilirubin increase:			
If normal at baseline: ALT or AST > 3 x ULN  If elevated at baseline: ALT or AST > 2 x baseline or > 300 U/L (whichever occurs first)	Normal For patients with Gilbert's syndrome: No change in baseline TBL	None	
 
• No change to study treatment
 
• Measure ALT, AST, ALP, GGT, TBL, direct and indirect bilirubin, PT/INR, albumin, CPK, and GLDH in 48-72 hours.
 
• Follow-up for symptoms.
 

ALT or AST	TBL	Liver Symptoms	Action
If normal at baseline: ALT or AST > 5 x ULN for more than two weeks  If elevated at baseline: ALT or AST > 3 x baseline or > 300 U/L (whichever occurs first) for more than two weeks	Normal  For patients with Gilbert's syndrome: No change in baseline TBL	None	
 
• Interrupt study drug
 
1. Measure ALT, AST, ALP, GGT, TBL, direct and indirect bilirubin, PT/INR, albumin, CPK, and GLDH in 48-72 hours.
 
• Follow-up for symptoms.
 
• Initiate close monitoring and workup for competing etiologies.
 
• Study drug can be restarted only if another etiology is identified and liver enzymes return to baseline.
 

If normal at baseline: ALT or AST > 8 x ULN	Normal	None	
ALT or AST increase with bilirubin increase:			
If normal at baseline: ALT or AST > 3 x ULN  If elevated at baseline: ALT or AST > 2 x baseline or > 300 U/L (whichever occurs first)	TBL > 2 x ULN (or INR > 1.5)  For patients with Gilbert's syndrome: Doubling of direct bilirubin	None	
If normal at baseline: ALT or AST > 3 x ULN  If elevated at baseline: ALT or AST > 2 x baseline or > 300 U/L (whichever occurs first)	Normal or elevated	Severe fatigue, nausea, vomiting, right upper quadrant pain	

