**Table 16-5 Follow up requirements for liver laboratory triggers**

Criteria	Actions required	Follow-up monitoring
Total Bilirubin (isolated)		
>1.5 – 3.0 ULN	
 
• Maintain treatment
 
• Repeat LFTs within 48-72 hours
 
	Monitor LFTs weekly until resolution a to ≤ Grade 1 or to baseline
> 3 - 10 × ULN (in the absence of known Gilbert syndrome)	
 
• Interrupt treatment
 
• Repeat LFT within 48-72 hours
 
	Monitor LFTs weekly until resolution a to ≤ Grade 1 or to baseline (ALT, AST, total

Criteria	Actions required	Follow-up monitoring
	
 
• Hospitalize if clinically appropriate
 
• Establish causality
 
• Record the AE and contributing factors (e.g. conmeds, med hx, lab) in the appropriate eCRF
 
	bilirubin, Alb, PT/INR, ALP and GGT) Test for hemolysis (e.g. reticulocytes, haptoglobin, unconjugated [indirect] bilirubin)
> 10 x ULN	
 
• Discontinue the study treatment immediately
 
• Hospitalize the participant
 
• Establish causality
 
• Record the AE and contributing factors(e.g. conmeds, med hx, lab) in the appropriate eCRF
 
	ALT, AST, total bilirubin, Alb, PT/INR, ALP and GGT until resolution c (frequency at investigator discretion)
Any AE potentially indicative of a liver toxicity*	
 
• Consider study treatment interruption or discontinuation
 
• Hospitalization if clinically appropriate
 
• Establish causality
 
• Record the AE and contributing factors(e.g., conmeds, med hx, lab) in the appropriate eCRF
 
	Investigator discretion

aResolution is defined as an outcome of one of the following: (1) return to baseline values, (2) stable values at three subsequent monitoring visits at least 2 weeks apart, (3) remain at elevated level after a maximum of 6 months, (4) liver transplantation, and (5) death.

Based on investigator's discretion investigation(s) for contributing factors for the liver event can include: Serology tests, imaging and pathology assessments, hepatologist's consultancy; obtaining more detailed history of symptoms and prior or concurrent diseases, history of concomitant drug use, exclusion of underlying liver disease.

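### After a Table 16-4 transaminase trigger, Protocol 6.5.1 leaves restarting inclisiran to the investigator, while Table 16-4 bars restart unless another cause is found

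*Protocol*

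**What the plan says.** Protocol 6.5.1 states that inclisiran "should be temporarily interrupted or permanently discontinued in participants with" any of three findings: intolerable adverse events, certain liver values, and unexplained CPK elevations with muscle symptoms or new renal dysfunction. The liver item reads "Liver laboratory values meeting the study drug interruption criteria listed in Table 16-4 and Table 16-5". A single restart sentence then covers all three: "Study treatment may be restarted at the discretion of the investigator, if the reason for discontinuation has resolved".

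Table 16-4 (Appendix 2) sets out what to do after transaminase triggers. Its first row leaves study treatment unchanged. The next row covers ALT or AST above 5 x ULN for more than two weeks (if elevated at baseline, above 3 x baseline or above 300 U/L for the same time), with normal bilirubin and no symptoms. Beside it stands the instruction to interrupt the drug, with this condition: "Study drug can be restarted only if another etiology is identified and liver enzymes return to baseline".

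Table 16-5 deals with isolated bilirubin. For values above 3 and up to 10 x ULN it says "Interrupt treatment", and it gives no restart rule.

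Section 6.5, which comes before all of this, says "Dose interruptions for the investigational study medication (inclisiran) are not permitted" and names no exception.

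**The concern.** A site that holds inclisiran for a liver trigger has two restart rules. One asks only whether the reason has resolved. The other also asks whether something other than the drug explains the finding. They part company when the enzymes settle and no explanation is found, which is the case where the study drug is hardest to rule out.

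Section 6.5.2.1 shows how seriously the protocol takes such cases. A confirmed combined rise in transaminases and bilirubin "with no other alternative cause for LFT abnormalities identified" must be reported as an SAE of potential treatment-induced liver injury. At stake is whether a participant with an unexplained liver signal can be given the drug again, and whether sites would answer that question in the same way.

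**Working it through.** No figure in the plan needs reproducing. The check compares the texts and then counts doses.

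**1. The two rules applied to one participant.** Baseline ALT is normal. ALT then exceeds 5 x ULN for more than two weeks, the drug is held, ALT returns to baseline, and no other cause is found.

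| Question | Section 6.5.1 | Table 16-4 |
|---|---|---|
| Is this a reason to interrupt? | Yes, by reference to the table's interruption criteria | Yes |
| What does restart require? | The reason has resolved; investigator's discretion | Another cause identified and enzymes back to baseline |
| Is restart allowed here? | Yes | No |

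The enzyme condition overlaps with resolution in 6.5.1, so the cause condition is the real difference. The reason listed in 6.5.1 is the laboratory value itself, so its normalisation counts as resolution on the plain text.

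**2. How far the conflict reaches.** Table 16-4 has five rows: one with no change to treatment and four that appear to be interruption rows. In the text available to us the action is printed once, beside the row for more than 5 x ULN lasting over two weeks. The action cells are blank for the other three: above 8 x ULN; above 3 x ULN (or the elevated-baseline equivalent) with raised bilirubin or INR; and the same transaminase threshold with severe symptoms. A merged cell is the likely explanation. The conflict is therefore shown directly for one row and probably holds for all four. Table 16-5 has no restart rule, so 6.5.1 governs there without conflict.

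**3. Size per participant.** Inputs:
- Doses on Days 0, 90 and 270, and end of study on Day 330 (Protocol Section 3 and Table 8-1).
- Missed-dose rule: "If a planned dose is missed by more than 3 months, start a new dosing schedule"; a dose less than 3 months late keeps the original schedule (Section 6.5).
- Assumptions: 3 months is taken as 90 days, and the 7-day visit window is ignored.

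| Trigger found | Further doses under 6.5.1 | Further doses under Table 16-4, no other cause |
|---|---|---|
| Before the Day 90 dose | up to 2 | 0 |
| Between the Day 90 and Day 270 doses | 1 | 0 |
| After the Day 270 dose | 0 | 0 |

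First line:
- Restart by Day 180 (180 − 90 = 90 days late) keeps the schedule: the late dose plus Day 270 gives 2.
- Restart on Days 181 to 240 begins a new schedule. The second dose falls between 181 + 90 = Day 271 and 240 + 90 = Day 330, again giving 2.
- Restart after Day 240 puts the second dose beyond Day 330 and gives 1.

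Second line: the Day 270 dose, on time or up to 330 − 270 = 60 days late, gives 1.

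**4. Which line applies in practice.** Table 8-1 schedules no chemistry between Day 0 and the Day 90 dosing visit, and 8.4.1 sends samples to a central laboratory. If the Day 90 result is not back before the injection, a trigger on scheduled testing is found after the Day 90 dose. The difference is then at most 1 dose. Reaching 2 needs an unscheduled test before the Day 90 dose.

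**The case against.** The strongest reply is that the rules can be read together. Section 6.5.1 gives a general permission and Table 16-4 a specific limit, so an investigator who follows the stricter rule breaks neither. Section 10.2.1 directs sites to Tables 16-4 and 16-5 for the actions to take after liver events, and the restart condition sits in the action column. Anyone applying the liver item of 6.5.1 has to open Table 16-4 anyway. Section 9.1.1 also requires study treatment to stop in any situation that might put the participant at risk, so 6.5.1 is not the only control on re-dosing.

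Much of this stands. It makes it likely that the stricter rule is intended, and it makes careless re-dosing less likely. It does not remove the conflict. Section 10.2.1 does not say that the table overrides 6.5.1, and the liver item in 6.5.1 takes only the interruption criteria from the tables. Section 9.1.1 rests largely on the investigator's judgement and contains no test of cause. A site relying on 6.5.1 could re-dose and be within the words of that section.

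**Conclusion.** The point holds as an inconsistency in a participant-safety instruction. It is directly shown for transaminases above 5 x ULN (or, if elevated at baseline, above 3 x baseline or above 300 U/L) lasting more than two weeks. It probably extends to the other three interruption rows if the action cell is merged. On scheduled testing it concerns at most one further dose per affected participant, assuming the Day 90 result arrives after the Day 90 injection. How many participants are affected cannot be estimated.

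A reader might infer more than the documents support:
- **That 6.5 forbids safety interruptions.** It does not do so in effect. Section 6.5 itself requires interruptions to be recorded, 6.5.1 and the liver tables direct them, and 8.4.1, 10.1.1 and 10.2.1 provide for them. This is a wording slip.
- **That a participant with an unexplained combined transaminase and bilirubin rise would be re-dosed.** The conflict for that row rests on the assumed merged cell, and 9.1.1 and SAE reporting also apply.
- **That the analyses are compromised.** The primary LDL-C analysis uses data after treatment discontinuation, and discontinuation is ignored as an intercurrent event for both primary variables. An effect on the Per-Protocol Set would need a safety hold to be graded a major deviation, and nothing says it would be. Restricted Set 2 drops inclisiran-arm participants with a missed dose by definition, however deviations are graded.

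**What to change.** In 6.5.1, after the restart sentence, add: *After an interruption triggered by Table 16-4, restart only under the conditions in Table 16-4.* Keep investigator discretion for the other reasons, including isolated bilirubin under Table 16-5.

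As a minor correction, reword 6.5 so that interruptions are not permitted except for the safety reasons in Section 6.5.1 and Appendices 2 and 3.

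The cost is one sentence, one clause and a letter to sites. The SAP is dated November 2023 and describes itself as finalised before database lock, so dosing may already be complete. In that case, check the dosing and liver-event records once before lock and list any participant re-dosed after a Table 16-4 interruption with no other cause recorded.

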## **6.5.2 Follow-up for toxicities**

### **6.5.2.1 Follow up on potential drug-induced liver injury (DILI) cases**

Participants with transaminase increase combined with total bilirubin increase may be indicative of potentially severe DILI, and should be considered as clinically important events and assessed appropriately to establish the diagnosis. The required clinical information, as detailed below, should be sought to obtain the medical diagnosis of the most likely cause of the observed laboratory abnormalities.

The threshold for potential DILI may depend on the participant's baseline AST/ALT and total bilirubin value; participants meeting any of the following criteria will require further follow-up as outlined below:

- For participants with normal ALT and AST and total bilirubin value at baseline: AST or ALT  $> 3.0 \times$  ULN combined with total bilirubin  $> 2.0 \times$  ULN
- For participants with elevated AST or ALT or total bilirubin value at baseline: [AST or ALT  $> 2 \times$  baseline] OR [AST or ALT  $> 300$  U/L] whichever occurs first combined with [total bilirubin  $> 2 \times$  baseline AND  $> 2.0 \times$  ULN]

A detailed history, including relevant information such as review of ethanol consumption, concomitant medications, herbal remedies, supplement consumption, history of any pre-existing liver conditions or risk factors, should be collected.

Laboratory tests should include ALT, AST, total bilirubin, direct and indirect bilirubin, gamma-glutamyl transferase (GGT), glutamate dehydrogenase (GLDH), prothrombin time (PT)/International Normalized Ratio (INR), alkaline phosphatase (ALP), albumin, and CPK.

Perform relevant examinations (Ultrasound or Magnetic resonance imaging (MRI), Endoscopic retrograde cholangiopancreatography (ERCP)) as appropriate, to rule out an extrahepatic cause of cholestasis. Cholestasis (is defined as an ALP elevation  $> 2.0 \times$  ULN with R value  $< 2$  in

participants without bone metastasis, or elevation of the liver-specific ALP isoenzyme in participants with bone metastasis).

Note: The R value is calculated by dividing the ALT by the ALP, using multiples of the ULN for both values. It denotes whether the relative pattern of ALT and/or ALP elevation is due to cholestatic ( $R \leq 2$ ), hepatocellular ( $R \geq 5$ ), or mixed ( $R > 2$  and  $< 5$ ) liver injury. For children, there are caveats to calculating the R-ratio as normal levels of ALP are higher than in adults with standard ranges varying by developmental age. In clinical situations where it is suspected that ALP elevations are from an extrahepatic source, the GGT can be used if available. GGT may be less specific than ALP as a marker of cholestatic injury, since GGT can also be elevated by enzyme induction or by ethanol consumption. It is more sensitive than ALP for detecting bile duct injury (<https://livertox.nih.gov/rucam.html>).

Table 6-3 provides guidance on specific clinical and diagnostic assessments which can be performed to rule out possible alternative causes of observed liver function test (LFT) abnormalities.

Table 6-3 Guidance on specific clinical and diagnostic assessments which can be performed to rule out possible alternative causes of observed LFT abnormalities

Disease	Assessment
Hepatitis A, B, C, E	IgM anti-HAV; HBsAg, IgM & IgG anti-HBc, HBV DNA; anti-HCV, HCV RNA, IgM & IgG anti-HEV, HEV RNA
CMV, HSV, EBV infection	IgM & IgG anti-CMV, IgM & IgG anti-HSV; IgM & IgG anti-EBV
Autoimmune hepatitis	ANA & ASMA titers, total IgM, IgG, IgE, IgA
Alcoholic hepatitis	Ethanol history, GGT, MCV, CD-transferrin
Nonalcoholic steatohepatitis	Ultrasound or MRI
Hypoxic/ischemic hepatopathy	Medical history: acute or chronic CHF, hypotension, hypoxia, hepatic venous occlusion. Ultrasound or MRI
Biliary tract disease	Ultrasound or MRI, ERCP as appropriate
Wilson disease (if <40 yrs old)	Caeruloplasmin
Hemochromatosis	Ferritin, transferrin
Alpha-1-antitrypsin deficiency	Alpha-1- antitrypsin

Other causes should also be considered based upon participants' medical history (hyperthyroidism / thyrotoxic hepatitis – T3, T4, TSH; CVD / ischemic hepatitis – ECG, prior hypotensive episodes; T1D / glycogenic hepatitis).

Following appropriate causality assessments, as outlined above, the causality of the treatment is estimated as “probable” i.e. >50% likely, if it appears greater than all other possible causes of liver injury combined. The term “treatment-induced” indicates *probably caused* by the treatment, not by something else, and only such a case can be considered a DILI case and should be reported as an SAE.

All cases confirmed on repeat testing meeting the laboratory criteria defined above, with no other alternative cause for LFT abnormalities identified, should be considered as “medically significant,” and thus, meet the definition of SAE and should be reported as SAE using the term “potential treatment-induced liver injury.” All events should be followed up with the outcome clearly documented.

## **6.6 Additional treatment guidance**

### **6.6.1 Treatment compliance**

Compliance will be ensured by the investigator and/or study personnel at each dosing visit. This information should be captured in the source document at each visit. Study drug (inclisiran) accountability will also be determined by the site monitor while performing routine site visits and at the completion of the study.

Duration of study drug exposure will be calculated based upon the dates recorded in the eCRF.

## **6.7 Preparation and dispensation**

Each study site will be supplied with study drug in packaging as described under investigational and control drugs section ([Section 6.1.1](#)).

A unique medication number is printed on the study medication label.

Investigator staff will identify the study medication kits to dispense to the participant by contacting the IRT and obtaining the medication number(s). The study medication has a 2-part label (base plus tear-off label), immediately before dispensing the medication kit to the participant, site personnel will detach the outer part of the label from the packaging and affix it to the source document.

As per [Section 4.6](#), during a Public Health Emergency that limits or prevents on-site study visits, a home health nurse is permitted to administer the study medication at a participant's home (if allowed by Local or Regional Health Authorities and Ethics Committees as appropriate) in the event the Investigator has decided that an on-site visit by the participant is no longer appropriate or possible. The dispatch of study medication from the site to the participant’s home remains under the accountability of the Investigator.

